# **1.3. Procedures in Case of Emergency**

Please reference the Manual of Procedures for detailed information on serious adverse event reporting.

## 2. SYNOPSIS

Name of Sponsor: Capricor, Inc.

Name of Investigational Product: CAP-1002 Allogeneic Cardiosphere-Derived Cells

Name of Active Ingredient: Cardiosphere-Derived Cells

**Title of Trial:** Open Label Extension of the Halt cardiomyOPathy progrEssion in Duchenne (HOPE-Duchenne) Trial

Trial Name: Halt cardiomyOPathy progrEssion in Duchenne (HOPE-OLE)

Trial Centers: Up to 3 (USA)

**Principal Investigators:** This is a multi-center trial with multiple Principal Investigators.

Studied Period: Approximately 6 months

**Phase of Development:** 2

#### **Objectives**:

*Primary*: To provide CAP-1002 to subjects who were randomized to the Usual Care Treatment Group of the HOPE-Duchenne trial and completed 12 months of follow-up.

*Secondary*: To explore the safety and efficacy of intravenous administration of CAP-1002 with repeat dose at Month 3.

**Methodology:** This Phase 2, multi-center, open label extension trial will provide CAP-1002 to subjects that were randomized to the Usual Care Treatment Group of the HOPE-Duchenne trial (CAP-1002-DMD-01) and explore the safety of two intravenous administrations of CAP-1002, each separated by three months. Subjects will undergo targeted tests and procedures during a 30-day screening period to determine eligibility based on protocol inclusion and exclusion criteria.

Eligible subjects will undergo baseline safety and efficacy assessments on Day 1 prior to their first infusion of CAP-1002. Administration of CAP-1002 (Day 1) should occur within a maximum of 14 days following confirmation of eligibility; if a delay of more than 14 days between enrollment and IP administration is unavoidable, a conversation between the Investigator and Medical Monitor should occur to determine the need for repeat assessments prior to infusion.

All CAP-1002 infusions will be conducted in an outpatient setting at the investigative site on Day 1 and Month 3. Subjects will be observed in the outpatient setting for at least two hours post infusion and then discharged the same day if medically cleared by the site Investigator.

A safety phone call will be performed 14 days ( $\pm 3$  days) after each CAP-1002 infusion, and if clinically indicated, an unscheduled in-person visit will be performed at the investigative site with targeted assessments based on presentation of signs and symptoms.

Blood samples will be collected before each CAP-1002 administration (Day 1 and Month 3), after each CAP-1002 infusion (Week 4 and Month 4) and at Month 6, unless otherwise indicated, for donor specific antibody (DSA) testing and routine serum chemistries, hematology and cardiac enzymes. HLA

typing will occur before the first CAP-1002 administration on Day 1. Collection will occur either at the investigative site or remotely at a designated central laboratory patient service center.

Trial visits at the investigative site will occur at Months 3 and 6 ( $\pm$ 14 days, respectively). Subjects will complete safety and efficacy assessments prior to CAP-1002 administration at the Month 3 trial visit.

The *primary safety endpoints* include the incidence of the following from baseline through the 6-month timepoint:

- Acute respiratory decompensation within 2 hours following IP administration
- Hypersensitivity reaction
  - Hypersensitivity reaction is defined as a clinical syndrome including, but not limited to, fever, leukocytosis, or rash with onset  $\leq 2$  hours post infusion and lasting < 24 hours, in the absence of clinical signs of concomitant infection.
- All-cause mortality
- Serious adverse events
- Treatment-emergent adverse events related to IP or administration procedure
- Immune sensitization syndrome
  - Immune sensitization syndrome shall be defined as: (a) clinical signs and symptoms consistent with systemic inflammation (e.g., fever, leukocytosis, rash, or arthralgia) with onset ≥ 24 hours post infusion and the absence of clinical signs of concomitant infection, AND (b) elevation of anti-human leukocyte antigen (HLA) antibodies against the donor cells (i.e., DSAs), detected ≤ 30 days following onset of syndrome, of (i) ≥ 2000 mean fluorescent intensity (MFI) if baseline MFI ≤ 1000, or (ii) ≥ 2 times baseline otherwise

The *exploratory endpoints* include the change from baseline to each assessment timepoint for the following assessments:

- All subjects
  - Mid-level (elbow) dimension of the Performance of Upper Limb (PUL) 1.2
  - Mid- and distal-level (elbow) dimension of the PUL 1.2
  - High-level (shoulder) dimension of the PUL 1.2
  - Left ventricular structure and function as assessed by cardiac MRI including regional systolic left ventricular wall thickening ejection fraction, end-diastolic volume, endsystolic volume, stroke volume, regional wall thickness, and circumferential strain
  - Slow vital capacity (SVC), forced expiratory volume in one second (FEV1), forced vital capacity (FVC), peak expiratory flow (PEF), maximum inspiratory pressure (MIP), maximum expiratory pressure (MEP), peak cough flow (PCF), and inspiratory flow reserve (IFR)
- Ambulatory subjects only

#### 6-Minute Walk Test (6MWT)

Oversight of the trial will be provided by the trial Steering Committee, an independent Data Safety Monitoring Board (DSMB), and an independent, Clinical Events Committee (CEC) that will adjudicate all potential primary safety endpoints.

Number of Subjects: Approximately 10 subjects will be enrolled

**Diagnosis and Main Criteria for Inclusion:** Subjects randomly assigned to the Usual Care Treatment Group of the HOPE-Duchenne trial and who completed the 12-month follow-up period will be evaluated for eligibility to participate in the Open Label Extension trial. Eligibility criteria will be assessed within 30 days prior to first infusion on Day 1 unless otherwise noted.

Inclusion Criteria:

- 1. Documented enrollment in the Usual Care Treatment Group of the HOPE-Duchenne trial and completion of trial follow-up through Month 12
- 2. Willing and able to provide informed consent to participate in the trial if  $\geq 18$  years of age, and assent with parental or guardian informed consent if < 18 years of age
- 3. Adequate venous access for intravenous CAP-1002 infusions and routine blood collections in the judgement of the Investigator
- 4. Assessed by the Investigator as willing and able to comply with the requirements of the trial

#### Exclusion Criteria:

- 1. Left ventricular ejection fraction (LVEF) < 35% within 6 months of screening
- 2. Planned or likely major surgery in the next 6 months after planned first infusion
- 3. Risk of near-term respiratory decompensation in the judgment of the investigator, *or* the need for initiation of non-invasive ventilator support as defined by serum bicarbonate ≥ 29 mmol/L at screening
- 4. History of non DMD-related chronic respiratory disease including, but not limited to, asthma, bronchitis, and tuberculosis
- 5. Acute respiratory illness within 30 days prior to screening
- 6. Known hypersensitivity to dimethyl sulfoxide (DMSO) or bovine products
- 7. Treatment with investigational product  $\leq 6$  months prior to first infusion
- 8. History, or current use, of drugs or alcohol that could impair ability to comply with participation in the trial
- 9. Inability to comply with the investigational plan and follow-up visit schedule for any reason, in the judgment of the investigator

#### Investigational Product, Dosage and Mode of Administration:

**Duration of Treatment:** CAP-1002 is administered as a single intravenous infusion on Day 1 and at Month 3 for a total of 2 administrations.

Duration of Trial: All subjects will be followed for 6 months post Day 1 infusion.

#### Criteria for evaluation:

#### Safety

Safety assessments at Week 4 and Months 3,4 and 6, unless otherwise indicated, will include the following: vital signs, height, weight, physical examination, 12-lead ECG, adverse events, DSA assessment, and clinical laboratory testing (serum chemistries, hematology, and cardiac enzymes). Adverse events and concomitant medications will also be collected during each 14-day post-infusion safety phone call, or if clinically indicated, an unscheduled in-person visit will be performed at the investigative site with targeted assessments based on presentation of signs and symptoms of subject.

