# 7. INVESTIGATIONAL PLAN

## 7.1. Overall Trial Design

This Phase 2, multi-center, open label extension trial will provide CAP-1002 to subjects who were randomized to the Usual Care Treatment Group and completed 12 months of follow-up in the HOPE-Duchenne trial. The trial will assess the safety of CAP-1002, administered as two IV infusions, each separated by 3 months. All subjects will undergo targeted tests and procedures within 30 days prior to first infusion, unless otherwise stated, to confirm eligibility based on protocol inclusion and exclusion criteria.

Eligible subjects will undergo baseline safety and efficacy assessments (Table 3) prior to the first infusion of CAP-1002. Administration of CAP-1002 (Day 1) should occur within a maximum of 14 days following confirmation of eligibility; if a delay of more than 14 days between enrollment and CAP-1002 administration is unavoidable, a conversation between the Investigator and Medical Monitor should occur to determine the need for repeat assessments prior to infusion. For the purposes of this trial, enrollment is defined as the time consent is signed.

All intravenous infusions will be conducted in an outpatient setting at the investigative site on Day 1 and at Month 3. Subjects will be observed in the outpatient setting for at least two hours post infusion and then discharged the same day if medically cleared by the site Investigator.

A safety phone call will be performed 14 days ( $\pm 3$  days) after each CAP-1002 infusion, and if clinically indicated, an unscheduled in-person visit will be performed at the investigative site with targeted assessments based on presentation of signs and symptoms.

Blood samples will be collected at Week 4 and Month 4 ( $\pm$ 7 days, respectively) for DSA testing and safety laboratory assessments. Collection will occur either at the investigative site or remotely at a designated central laboratory patient service center.

Subsequent trial visits at the investigative site will occur at Months 3 and 6 ( $\pm$ 14 days, respectively). Subjects will complete safety and efficacy assessments at each of these visits and prior to CAP-1002 administration in the case of the Month 3 trial visit.

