#### Table 3: Schedule of Assessments

Procedure / Event 	Screening	Day 1 (Infusion #1)	Post-Infusion #1 Safety Monitoring	Week 4	Month 3 (Infusion #2)	Post-Infusion #2 Safety Monitoring	Month 4	Month 6 / Early Termination 
Trial Day (Visit Window)	≤30 days prior to Day 1		14 days (±3) after Infusion #1	30 days (± 7)	90 days (±14)	14 days (±3) after Infusion #2	120 days (± 7)	180 (±14)
Informed Consent / Assent	х							
Eligibility Assessment	Х	Х						
Prior & Concomitant Meds	х	Х	х		х	х		Х
Medical History	Х							
Medical Status Questionnaire		х			х			х
Adverse Events	Х	Х	Х		Х	х		х
CAP-1002 IV Infusion 		Х			Х			
Post-Infusion Safety Call 4			Х			х		
Vital Signs		Х			Х			Х
Height / Ulna Length 		Х			Х			х
Weight		Х			Х			Х
Physical Examination		Х			Х			х
12-Lead ECG		Х			Х			х
Serum Chemistry 	Х	Х		Х	Х		Х	х
Hematology 		Х		Х	Х		Х	Х
Cardiac Enzymes 		Х			Х			Х
HLA Typing 		Х						

Protocol No. CAP-1002-DMD-03 Amendment 1.0

Procedure / Event 	Screening	Day 1 (Infusion #1)	Post-Infusion #1 Safety Monitoring	Week 4	Month 3 (Infusion #2)	Post-Infusion #2 Safety Monitoring	Month 4	Month 6 / Early Termination 
Trial Day (Visit Window)	≤30 days prior to Day 1		14 days (±3) after Infusion #1	30 days (± 7)	90 days (±14)	14 days (±3) after Infusion #2	120 days (± 7)	180 (±14)
Donor-Specific Antibodies 		х		Х	х		х	Х
PUL 1.2		Х			Х			Х
6-Minute Walk Test 		Х			Х			х
Pulmonary Function Testing 		х			х			Х
Cardiac MRI 	х							Х

 Sites will complete assessments in the following sequence: 1) safety and other trial assessments, excluding blood collection (e.g., vital signs, height, weight, 12-lead electrocardiogram [ECG], etc.), 2) pulmonary function testing (PFT), 4) PUL 1.2, 5) 6MWT, 6) blood collection, 7) cardiac MRI (if applicable), and 8) CAP-1002 Infusion (if applicable). All efforts must be made for the same clinical evaluator to complete assessments for the same subject at the same time of day throughout the trial (preferably in the morning).

 All attempts must be made to perform the trial assessments indicated for the Month 6 visit (i.e., final comprehensive visit) for subjects that decide to early terminate early from the trial after starting at least one CAP-1002 infusion.

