#### 13.1.5. Immunologic Assessments

Serum for DSA testing and whole blood for HLA typing will be collected following the standard institutional procedures for blood collection and submitted to a central laboratory for analysis. Instructions on collection, processing, storage and shipping the samples to the central laboratory are located in the Laboratory Manual.

DSA collection for the Week 4 and Month 4 ( $\pm$ 7 days, respectively) visits will occur either at the investigative site or remotely at a designated central laboratory patient service center.

DSA samples may also be collected in the setting of clinical suspicion of immune sensitization syndrome in the judgment of the Investigator. See Section 7.2.1 for additional details regarding immune sensitization syndrome as a safety endpoint.

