#### 13.2.6. Adverse Event Follow-up

All AEs are followed by the investigative site until an outcome is known or the subject's participation in the trial concludes at either 6 months or early termination, whichever occurs first.

The investigative site is expected to review all ongoing AEs at each visit. AEs are followed until resolution or until no further changes in the event are expected (i.e., the point at which a subject experiencing an AE is treated successfully and stabilized even though he may continue to experience lingering sequelae that may never resolve), or it is agreed that further follow-up of the event is not warranted (e.g., non-serious, IP unrelated, ongoing at final visit). See Section 13.2.3 for reporting ongoing AEs at the end of trial participation.

For SAEs that were incomplete or ongoing at the time of initial submission, the investigative site is required to submit follow-up SAE Report Forms when event information is available to the research site personnel and/or an outcome is known.

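### No adverse event query is scheduled at the Week 4 and Month 4 blood draws, although the synopsis lists one, so about 76 days separate each 14-day call from the next scheduled query

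*Protocol*

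**What the plan says.** - **Protocol synopsis, Criteria for evaluation, Safety.** The sentence opens "Safety assessments at Week 4 and Months 3,4 and 6, unless otherwise indicated, will include the following" and goes on to list "vital signs, height, weight, physical examination, 12-lead ECG, adverse events, DSA assessment, and clinical laboratory testing". For the 14-day calls, the synopsis separately mentions adverse events and concomitant medications.
- **Protocol Table 3, repeated in SAP Appendix B.** The row "Adverse Events" is marked at Screening, Day 1, both 14-day calls, Month 3 and Month 6. It is blank at Week 4 and Month 4, and so is the concomitant medications row. The row "Donor-Specific Antibodies" is marked at Day 1, Week 4, Month 3, Month 4 and Month 6. Hematology follows the same pattern, and serum chemistry adds Screening.
- **Protocol 7.1 and SAP section 3.** "Blood samples will be collected at Week 4 and Month 4", for DSA and safety laboratory tests, at the site or at a remote laboratory center.
- **Protocol 13.1.** Safety assessments follow Table 3.
- **Protocol 13.1.5.** The Week 4 and Month 4 collections are called visits. In addition, "DSA samples may also be collected in the setting of clinical suspicion of immune sensitization syndrome".
- **Protocol 13.2.4 and 13.2.6.** Adverse events are collected from consent to six months, and "The investigative site is expected to review all ongoing AEs at each visit".
- **Protocol 12.3.** Medications are reviewed at each trial visit.
- **Protocol 7.2.1 and SAP 2.2.1.** Immune sensitization syndrome is a primary safety endpoint with two required parts: inflammatory signs starting at least 24 hours after infusion without signs of infection, and a DSA rise detected no more than 30 days after onset.

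**The concern.** The summary and the operative schedule give different answers to a simple question: is the family asked about symptoms at Week 4 and Month 4? If sites follow Table 3, they are not. Those are two of the four scheduled post-infusion DSA draws, and the only two that are not also site visits.

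Immune sensitization syndrome cannot be classified from DSA alone. It needs a clinical picture, a judgment that infection was absent, and an onset date from which to count 30 days. Related treatment-emergent adverse events, another primary safety endpoint, also depend on symptoms being reported. Fever, rash or joint pain that starts after the 14-day call and resolves is first asked about weeks later, when both the event and its date may be poorly recalled.

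SAP 5.8 plans to analyze DSA in the context of the syndrome only if a case occurs, so a missed symptom report would also remove that analysis. With up to 10 subjects, one case is 1/10, or 10 percentage points, of the reported incidence.

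**Working it through.** The documents state no gap length, so there is no figure to reproduce. The check is date arithmetic on Table 3, counting days from the first infusion.

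**Inputs (Table 3).** Calls at 14 ± 3 days after each infusion; Week 4 at day 30 ± 7; Month 3 and infusion 2 at day 90 ± 14; Month 4 at day 120 ± 7; Month 6 at day 180 ± 14.

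**Scheduled interval without an adverse event query**

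| Interval | Nominal | Shortest | Longest |
|---|---|---|---|
| Call 1 to Month 3 | 90 − 14 = 76 | 76 − 17 = 59 | 104 − 11 = 93 |
| Call 2 to Month 6 | 180 − (90 + 14) = 76 | 166 − (104 + 17) = 45 | 194 − (76 + 11) = 107 |

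Together the nominal gaps cover 2 × 76 = 152 of 180 days, or 84%. If infusion 1 is taken as Day 1, as in SAP 4.2, and Month 3 as study day 90, call 1 falls on Day 15 and the first gap is 90 − 15 = 75 days. Nothing turns on that day.

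**Pairing with DSA.** Take onset on day 20. The Week 4 draw comes 30 − 20 = 10 days later, inside the 30-day limit. The first scheduled question about symptoms comes 90 − 20 = 70 days later. After infusion 2, onset on day 110 gives 120 − 110 = 10 days to the draw and 180 − 110 = 70 days to the question. At nominal days, any onset between a call and the next draw is at most 30 − 14 = 16 (or 120 − 104 = 16) days before that draw. The laboratory part of the definition is therefore available on time and the symptom query is late.

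**With a query at both draws.** Each 76-day gap splits into 16 + 60 days: 30 − 14 and 90 − 30, then 120 − 104 and 180 − 120. The longer piece ranges from 76 − 37 = 39 to 104 − 23 = 81 days after Week 4, and from 166 − 127 = 39 to 194 − 113 = 81 days after Month 4.

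**One detail on windows.** Month 4 is counted from Day 1 and call 2 from infusion 2. Month 4 minus call 2 therefore runs from 113 − 121 = −8 to 127 − 87 = 40 days. At one extreme the call follows the draw and already supplies a nearby symptom query.

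**The case against.** The strongest reply is that the schedule is consistent once its order of precedence is respected. The synopsis sentence carries a qualifier, section 13.1 defers to Table 3, and section 7.1 and SAP section 3 describe these timepoints as blood collections. The same synopsis list includes vital signs, height, weight, physical examination and ECG, which Table 3 also omits there, so it reads as a pooled summary. This stands as far as it goes: there is no flat contradiction. It leaves the gap in place, because Table 3 is then the plan that sites will follow.

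A reader might infer more than the documents support:

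- **That adverse events go unmonitored for 76 days.** Only a scheduled query is missing. Collection is continuous under 13.2.4, unscheduled visits are allowed, and DSA can be drawn on suspicion. After the call, however, these routes depend largely on families volunteering symptoms.
- **That section 13.2.6 already requires a query for new events.** It covers ongoing events. Because 13.1.5 calls these draws visits, follow-up of known events is arguably due there, but asking about new ones is not.
- **That no clinical information is collected at these draws.** Leukocytosis is a named sign in the definition, and a blood count is taken. What is missing is the symptom history and the clinical check for infection.
- **That the amendment dropped the query.** The Amendment 1.0 log records removal of CK-MB and troponin I at these timepoints and says nothing about adverse events. A list of changes that is silent on an item shows no recorded change to it.
- **That incidence will be under-counted.** The documents hold no data on recall. A day-20 symptom remembered at day 90 can still be matched to the day-30 DSA result.

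It is also fair to say that the trial is small and descriptive, with no formal hypotheses, and that an added query has limited reach. A symptom starting on day 35 would still first be asked about near day 90.

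**Conclusion.** The point holds as a mismatch to reconcile, with a modest practical consequence. Under Table 3 and SAP Appendix B as written, the Week 4 and Month 4 DSA and hematology draws have no paired symptom query. The scheduled interval without an adverse event query is 76 days after each call (59 to 93 and 45 to 107 days with windows).

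The possible effect is under-ascertainment, or imprecise onset dates, for mild symptoms arising after the call. It bears mainly on immune sensitization syndrome and also on related treatment-emergent events. Its size cannot be derived from the documents.

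The conclusion assumes that sites follow Table 3 literally, hold both 14-day calls, and have no unscheduled contact in between. It does not depend on treating the synopsis as binding.

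**What to change.** Bring the synopsis, Table 3 and SAP Appendix B into agreement by marking adverse events at Week 4 and Month 4. Collect them by telephone when the draw is remote, and record the onset date of each symptom. Mark concomitant medications at the same two timepoints. The basis for that entry is section 12.3, which reviews medications at each trial visit; the synopsis does not list medications there. The remaining synopsis items that Table 3 leaves blank at these timepoints should be corrected in the same edit, so that the sentence and the schedule agree.

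The main gain is a symptom history taken alongside each DSA result. The longest nominal interval without a query falls from 76 to 60 days (39 to 81 with windows), so the gap is shortened but not closed. The cost is at most 2 × 10 = 20 short calls of coordinator time. The change adds data collection only.

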#### Efficacy

The following efficacy outcome measures will be performed at Months 3 and 6 unless otherwise specified: PUL 1.2, spirometry, 6MWT when deemed appropriate by the Investigator, and cardiac MRI.

#### **Statistical Methods:**

#### Sample Size

Up to 10 subjects that were randomized to Usual Care Treatment Group and completed the 12-month follow-up period for the HOPE-Duchenne trial will be enrolled in this trial.

#### Analysis Populations

Intent-to-Treat (ITT) Population: All patients who meet the enrollment criteria and are enrolled in the trial. These patients will also constitute the Safety population.

Per Protocol (PP) Population: All enrolled subjects who have no protocol deviations/violations that could significantly impact completeness, accuracy, and/or reliability of the trial data. The list of subjects in the per protocol population will be compiled prior to database lock.

